Clinical Trial Protocol

Document Number: c11428532-01

BI Trial No.: 1386-0007

BI Investigational Product: BI 1467335

Title: Safety, tolerability, pharmacokinetics and pharmacodynamics of multiple rising oral doses of BI 1467335 in healthy Japanese male volunteers with multiple oral doses at the highest dose in Caucasian for comparison (randomised, double-blind, placebo-controlled trial)

Lay Title: This study tests BI 1467335 in healthy Japanese and Caucasian men. The study tests how different doses of BI 1467335 are taken up in the body and how well they are tolerated.

Clinical Phase: I

Trial Clinical Monitor:

Phone:
Fax:

Co-ordinating Investigator:

Phone:
Fax:

Status: Final Protocol

Version and Date: Version: 1.0 Date: 11 May 2017

Page 1 of 78

Proprietary confidential information

© 2017 Boehringer Ingelheim International GmbH or one or more of its affiliated companies. All rights reserved.
This document may not - in full or in part - be passed on, reproduced, published or otherwise used without prior written permission

CLINICAL TRIAL PROTOCOL SYNOPSIS

Name of company: Boehringer Ingelheim		Tabulated Trial Protocol		
Name of finished product: Not applicable				
Name of active ingredient: BI 1467335				
Protocol date: 11 May 2017	Trial number: 1386-0007		Revision date: Not Applicable	
Title of trial: Safety, tolerability, pharmacokinetics and pharmacodynamics of multiple rising oral doses of BI 1467335 in healthy Japanese male volunteers with multiple oral doses at the highest dose in Caucasian for comparison (randomised, double-blind, placebo-controlled trial)				
Co-ordinating Investigator:				
Trial site:				
Clinical phase: I				
Objectives: To investigate the safety, tolerability, pharmacokinetics and pharmacodynamics following multiple rising oral doses of BI 1467335 in healthy Japanese male volunteers with single dose Caucasian group for comparison				
Methodology: Multiple rising oral doses in Japanese with single dose Caucasian group for comparison, randomised, double-blind, placebo controlled within dose groups, multiple centres.				
No. of subjects:				
total entered: 48 (36 Japanese and 12 Caucasian)				
each treatment: 12 per dose group /ethnicity (9 on active and 3 on placebo)				
Diagnosis: Not applicable				
Main criteria for inclusion: Healthy male Japanese and Caucasian subjects Age \geq 20 and \leq 45 years BMI range: \geq 18.5 and \leq 25 kg/m ² (Japanese), \geq 18.5 and \leq 29.9 kg/m ² (Caucasian)				
Test product: BI 1467335 film-coated tablets				
dose: 3, 6 and 10 mg qd (Japanese) and 10 mg qd (Caucasian)				
mode of admin.: Oral administration with 240 mL water after an overnight fast of at least 10 hours				
Comparator product: Placebo				
dose: Not applicable (matching placebo tablets)				
mode of admin.: Oral administration with 240 mL water after an overnight fast of at least 10 hours				
Duration of treatment: 28 days with multiple oral doses of BI 1467335 q.d.				

Proprietary confidential information © 2017 Boehringer Ingelheim International GmbH or one or more of its affiliated companies

Name of company: Boehringer Ingelheim		Tabulated Trial Protocol		
Name of finished product: Not applicable				
Name of active ingredient: BI 1467335				
Protocol date: 11 May 2017	Trial number: 1386-0007		Revision date: Not Applicable	
Criteria for pharmacokinetics: Secondary endpoints: After the first dose: AUC ₀₋₂₄ and C _{max} of BI 1467335 After the last dose: AUC _{0-24,28} and C _{max,28} of BI 1467335				
Criteria for pharmacodynamics:				
Criteria for safety: Primary endpoint: The number [N (%)] of subjects with drug-related AEs				
Statistical methods: Descriptive statistics will be calculated for all endpoints. Dose proportionality of BI 1467335 will be explored using a regression model; a 95% confidence interval for the slope will be computed.				

Proprietary confidential information © 2017 Boehringer Ingelheim International GmbH or one or more of its affiliated companies

FLOW CHART

Visit	Day	Planned time (relative to first drug administration [h:min])	Approximate clock time of actual day [h:min]	Event and comment	Safety laboratory	PK blood ⁹			12-lead ECG ⁸	Vital signs (BP, PR)	Questioning for AEs and concomitant therapy ⁶
1	-28 to -2			Screening (SCR) ^{1, 5, 12}	x ⁵				x	x	
2	-3 to -1 ⁷	-48:00	09:00	Ambulatory visit	x				x	x	x
	-1	-12:00	21:00	Admission to trial site	x ⁵						x
1	1	-2:00	07:00	Allocation to treatment ²	x ^{2,13}			x ^{2, 16}	x ²	x ²	x ²
		-0:05	08:55			x ¹⁴	x ¹⁰				
		0:00	09:00	First drug administration			▲				
		0:15	09:15		x			x			
		0:30	09:30		x			x	x		
		0:45	09:45		x			x	x		
		1:00	10:00		x			x	x	x	
		1:30	10:30		x			x			
		2:00	11:00	240 mL fluid intake and light breakfast ³	x			x	x	x	
		3:00	12:00		x						
		4:00	13:00	240 mL fluid intake, thereafter lunch ³	x	+		x	x	x	
		6:00	15:00		x						
		8:00	17:00	Snack (voluntary) ³	x	+		x	x	x	
		10:00	19:00	Dinner ³	x						
		12:00	21:00		x	+		x	x	x	
	2	23:55	08:55		x ¹⁴	▼	x ¹⁴	x ²	x ²	x ²	
		24:00	09:00	Drug administration ¹¹							
3	48:00	09:00		Drug administration ¹¹	x			x ²	x ²	x ²	
4		71:55	08:55			x ¹⁴					
		72:00	09:00	Drug administration ¹¹				x ²	x ²	x ²	
		72:30	09:30		x						
		73:00	10:00	Discharge from trial site (confirmation of fitness) ⁴	x			x	x	x	
7	7	143:55	08:55	Ambulatory visit	x ¹⁴		x ¹⁴				
		144:00	09:00	Drug administration ¹¹	x ²			x ²	x ²	x ²	
		144:30	9:30		x						
		145:00	10:00	Discharge	x			x	x		

Proprietary confidential information © 2017 Boehringer Ingelheim International GmbH or one or more of its affiliated companies

Visit	Day	Planned time (relative to first drug administration [h:min])	Approximate clock time of actual day [h:min]	Event and comment	Safety laboratory	PK _{blood} ⁹			12-lead ECG ⁸	Vital signs (BP, PR)	Questioning for AEs and concomitant therapy ⁶
2	13	300:00	21:00	Admission to trial site							
	14	310:00	07:00		x ²				x ²	x ²	x ²
		311:55	08:55		x ¹⁴		x ¹⁴				
		312:00	09:00	Drug administration		▲					
		312:15	09:15		x			x			
		312:30	09:30		x			x	x		
		312:45	09:45		x			x	x		
		313:00	10:00		x			x	x	x	
		313:30	10:30		x			x			
		314:00	11:00	240 mL fluid intake and light breakfast ³	x			x	x	x	
		315:00	12:00		x						
		316:00	13:00	240 mL fluid intake, thereafter lunch ³	x	+		x	x	x	
		318:00	15:00		x						
		320:00	17:00	Snack (voluntary) ³	x	+		x	x	x	
		322:00	19:00	Dinner ³	x						
		324:00	21:00		x	+		x	x	x	
	15	335:55	08:55		x ¹⁴	▼					
		336:00	09:00	Drug administration ¹¹				x ²	x ²	x ²	
		336:30	09:30		x						
		337:00	10:00	Discharge	x			x	x		
	21	479:55	08:55	Ambulatory visit	x ¹⁴		x ¹⁴				
		480:00	09:00	Drug administration ¹¹	x ²			x ²	x ²	x ²	
		480:30	09:30		x						
		481:00	10:00	Discharge	x			x	x	x	
	26	599:55	08:55	Admission to trial site	x ¹⁴						
		600:00	09:00	Drug administration ¹¹				x ²	x ²	x ²	
		600:30	09:30		x						
		601:00	10:00		x			x	x	x	
		612:00	21:00								
	27	623:55	08:55		x ¹⁴						
		624:00	09:00	Drug administration ¹¹		▲		x ²	x ²	x ²	
		624:30	09:30		x						
		625:00	10:00		x			x	x	x	

Proprietary confidential information © 2017 Boehringer Ingelheim International GmbH or one or more of its affiliated companies

Visit	Day	Planned time (relative to first drug administration [h:min])	Approximate clock time of actual day [h:min]	Event and comment	Safety laboratory	PK _{blood} ⁹			12-lead ECG ⁸	Vital signs (BP, PR)	Questioning for AEs and concomitant therapy ⁶
2	28	646:00	7:00		x ²				x ²	x ²	x ²
		647:55	08:55		x ^{14, 15}	▼	x ^{14, ,16}				
		648:00	09:00	Last drug administration		▲					
		648:15	09:15		x				x		
		648:30	09:30		x ¹⁵		x	x	x	x	
		648:45	09:45		x				x	x	
		649:00	10:00		x ¹⁵		x	x	x	x	x
		649:30	10:30		x				x		
		650:00	11:00	240 mL fluid intake and light breakfast ³	x ¹⁵		x	x	x	x	x
		651:00	12:00		x						
		652:00	13:00	240 mL fluid intake, thereafter lunch ³	x ¹⁵	+	x	x	x	x	x
		654:00	15:00		x ¹⁵		x				
		656:00	17:00	Snack (voluntary) ³	x ¹⁵	+		x	x	x	x
		658:00	19:00	Dinner ³	x ¹⁵		x				
		660:00	21:00		x ¹⁵	+	x	x	x	x	x
	29	672:00	09:00		x ¹⁵	▼	x	x	x	x	x
		673:00	10:00	Discharge from trial site (confirmation of fitness) ⁴							
30	696:00	09:00	Ambulatory visit ¹⁷	x	x ¹⁵		x	x	x	x	x
32+-1	744:00	09:00	Ambulatory visit ¹⁷		x ¹⁵		x				x
36+-2	840:00	09:00	Ambulatory visit ¹⁷		x ¹⁵		x				
40	936:00	09:00	Ambulatory visit		x ¹⁵		x				
3	42 to 48		End of trial (EOT) examination ^{4,12}	x				x	x	x	x

1. Screening includes subject information, informed consent, physical examination, check of vital signs, ECG, safety laboratory (including exclusionary laboratory tests), demographics (including determination of body height and weight, smoking status and alcohol history), relevant medical history, concomitant therapy and review of inclusion/exclusion criteria.
2. The time is approximate; the respective procedure is to be performed and completed within 3 h prior to drug administration. Allocation to treatment may be performed at any time following enrolment but must be completed prior to (first) drug administration.
3. If several actions are indicated at the same time point, the intake of meals will be the last action.
4. End of trial examination includes physical examination, body weight, vital signs, ECG, safety laboratory, recording of AEs and concomitant therapies. Confirmation of fitness includes physical examination.
5. Urine drug screening and alcohol breath test will be done at screening and Day -1.
6. AEs and concomitant therapies will be recorded throughout the trial, but will be specifically asked for at the time points indicated in the [Flow Chart](#) above.
7. Safety laboratory, ECG, blood pressure assessment and AE questioning to be done and medically evaluated within 3 days prior to first administration of study drug; this visit can be omitted, if the screening examination is performed on Days -3, -2 or -1.
8. The ECG recording has to be performed as triple on Day 1 and Day 2, Day 14 and Day 15, Day 28 and Day 29. All other ECG recordings will be single ECGs.
9. Sampling times and periods may be adapted based on information obtained during the trial (e.g. preliminary PK data) including addition of samples and visits as long as the total blood volume taken does not exceed 400 mL per subject.

Proprietary confidential information © 2017 Boehringer Ingelheim International GmbH or one or more of its affiliated companies

11. Administration under fasting conditions. On the hospitalization days, light breakfast (or snack) 2 h after drug administration
12. Ophthalmological examinations (exclusion of cataract).Slit lamp test can be performed during screening or until Day -1 and from Day 29 to EOT visit.
14. Samples to be drawn immediately (within 30 minutes) prior to drug administration.
15. Additional blood samples for metabolite analysis.

17. If consecutive two-day ambulatory visits take place, subjects can stay at the site.

TABLE OF CONTENTS

TITLE PAGE	1
CLINICAL TRIAL PROTOCOL SYNOPSIS	2
FLOW CHART	4
TABLE OF CONTENTS	8
ABBREVIATIONS	12
2. RATIONALE, OBJECTIVES, AND BENEFIT - RISK ASSESSMENT	26
2.2 TRIAL OBJECTIVES.....	27
3. DESCRIPTION OF DESIGN AND TRIAL POPULATION.....	31
3.1 OVERALL TRIAL DESIGN AND PLAN	31
3.1.1 Administrative structure of the trial	32
3.2 DISCUSSION OF TRIAL DESIGN, INCLUDING THE CHOICE OF CONTROL GROUP	32
3.3 SELECTION OF TRIAL POPULATION	33
3.3.1 Main diagnosis for study entry	33
3.3.2 Inclusion criteria	33
3.3.3 Exclusion criteria	34
3.3.4 Removal of subjects from therapy or assessments.....	35
3.3.4.1 Removal of individual subjects.....	35
3.3.4.2 Discontinuation of the trial by the sponsor	36
3.3.5 Replacement of subjects	36
4. TREATMENTS.....	37
4.1 TREATMENTS TO BE ADMINISTERED	37
4.1.1 Identity of BI investigational product and comparator product.....	37
4.1.2 Method of assigning subjects to treatment groups	37
4.1.3 Selection of doses in the trial.....	38
4.1.4 Drug assignment and administration of doses for each subject	38

Proprietary confidential information © 2017 Boehringer Ingelheim International GmbH or one or more of its affiliated companies

4.1.5	Blinding and procedures for unblinding	39
4.1.5.1	Blinding.....	39
4.1.5.2	Procedures for emergency unblinding	39
4.1.6	Packaging, labelling, and re-supply	40
4.1.7	Storage conditions.....	40
4.1.8	Drug accountability	40

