4.2.2.2 Restrictions on diet and life style

While admitted to the trial site the subjects are restricted from consuming any other foods or drinks than those provided by the staff. Standardised meals will be served at the time points described in the [Flow Chart](#) during in-house days.

From Day 1 to Day 28, no food is allowed for at least 10 h before and 2 h after administration of the study drug.

From 1 hour before drug intake in the morning of PK profiling days 1, 14 and 28, liquid intake will be restricted to the water administered with the drug and 240 mL of water at 2 hours and 4 hours post-dose (mandatory for all subjects). From lunch until 24 hours post-dose fluid intake is restricted within 3000 mL.

Proprietary confidential information © 2017 Boehringer Ingelheim International GmbH or one or more of its affiliated companies

Alcoholic beverages, grapefruits, Seville oranges (sour or bitter oranges) and their juices, and dietary supplements and products including St. John's wort (*Hypericum perforatum*) are not permitted starting 7 days before the first administration of trial medication until after the last PK sample is collected.

nicotine-containing products (e.g., cigarettes, cigars, chewing tobacco, snuff) should be stopped at least 6 weeks before screening and abstained from using these products until study completion.

Methylxanthine-containing drinks or foods (such as coffee, tea, cola, energy drinks, and chocolate) are not permitted 24 hours preceding the administration of trial medication and until the in-house period at the trial site. On the ambulatory days, it is restricted up to max 200 ml (coffee, tea, cola, energy drinks), or 50 g (chocolate and chocolate products).

Excessive physical activity (such as competitive sport) should be avoided starting 7 days before the first administration of trial medication until the EOT examination.

Direct exposure to the sun or exposure to solarium radiation should be avoided during the entire study.

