5.2.3 Assessment of safety laboratory parameters

A total amount of up to approximately 120 mL blood will be taken per subject during the whole course of the study for safety laboratory parameters. This amount may be exceeded if unscheduled (additional) monitoring including retest of laboratory results is warranted.

For the assessment of laboratory parameters, blood and urine samples will be collected by the trial site at the time points indicated in the [Flow Chart](#) after the subjects have fasted for at least 10 hours. Overnight fasting is not required at the discretion of the investigator or designate for retests.

The parameters that will be determined are listed in [Tables 5.2.3: 1](#) and [5.2.3: 2](#). Reference ranges will be provided in the ISF, [Section 10](#).

Proprietary confidential information © 2017 Boehringer Ingelheim International GmbH or one or more of its affiliated companies

Manual differential white blood cell count or urine sediment examinations will only be performed if there is an abnormality in the automatic blood cell count or in the urinalysis and it is deemed clinically necessary by the investigator, respectively.

Table 5.2.3: 1 Routine laboratory tests

Functional lab group	Test name
Haematology	Haematocrit Haemoglobin Red blood cell count (RBC) Reticulocyte count White blood cell count (WBC) Platelet count
Automatic WBC differential (relative) ¹	Neutrophils, eosinophils, basophils, monocytes, lymphocytes
Coagulation	Activated partial thromboplastin time (aPTT) Prothrombin time (INR) (ratio) Fibrinogen
Enzymes	Aspartate transaminase (AST/GOT) Alanine transaminase (ALT/GPT) Alkaline phosphatase (ALP) Gamma-glutamyl transferase (GGT/γ-GT) Creatine kinase (CK) CK-MB, only if CK is elevated Lactate dehydrogenase (LDH) Lipase Amylase
Hormones ²	Thyroid stimulating hormone (TSH)
Substrates	Serum glucose Creatinine Blood Urea Nitrogen (BUN) Total bilirubin Direct bilirubin Total protein Albumin C-Reactive Protein (CRP) Uric acid Total cholesterol Triglycerides
Electrolytes	Sodium Potassium Calcium

Table 5.2.3: 1 Routine laboratory tests (cont.).

Functional lab group	Test name
Urinalysis (strip or dipstick)	Urine nitrite Urine protein Urine glucose Urine ketone Urobilinogen Urine bilirubin Urine erythrocytes Urine leukocytes Urine pH
Urine sediment ³	Only positive findings will be reported (for instance, the presence of sediment bacteria, casts in sediment, squamous epithelial cells, erythrocytes, leukocytes)

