6. INVESTIGATIONAL PLAN

6.1 VISIT SCHEDULE

All visits must be performed as specified in Flow Chart. The investigator/sponsor can decide to perform an unscheduled visit if deemed necessary for any valid reasons.

Further details of measurement performed during the study are specified under [Section 5](#).

Time windows are permitted as follows:

- General medical examination: at screening (1 to 21 days prior to Day1) and at the end-of-trial evaluation (within 14 to 20 days after last drug administration).
- BP and PR: ± 15 min (0:30, 0:45, 1:00, 2:00) and ± 30 min (4:00, 8:00, 12:00) on Day 1, Day 14 and Day 28, ± 60 min on other days and up to 3 hours prior to drug administration if indicated "before drug administration"
- ECG: ± 15 min (0:15, 0:30, 0:45, 1:00, 1:30, 2:00) and ± 30 min (4:00, 8:00, 12:00) on Day 1, Day 14 and Day 28, ± 60 min on other days.
ECGs on Day 1, 2, 14, 15, 28 and 29: for the second and third ECG a time interval of 1-3 min between ECGs should be maintained
- Laboratory/urinalysis: Up to 3 hours prior to drug administration if indicated "before drug administration". Urinalysis test can be done up to 3 hours prior to drug administration at some other time points indicated in the flow chart.
- Pharmacokinetic blood sampling for predose concentration in multiple dose part: ± 5 min (has to be done before drug administration)

Other pharmacokinetic blood sampling / urine collection: For planned individual plasma concentration sampling times refer to Flow Chart. While these nominal times should be adhered to as closely as possible, the actual sampling times will be recorded and used for the calculation of pharmacokinetic parameters.

The designation "before" on Day 1 refers to the time period of 3 hours before drug administration (see [Flow Chart](#)), i.e., study measurements and assessments scheduled to occur "before" have to be performed and completed within 3 hours prior to drug administration.

Relevant time violations will be identified and their handling discussed no later than at the (B)RPM.

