## **7.8.2     Laboratory data**

The analyses of laboratory data will be descriptive in nature and will be based on BI standards ([7](#)). Laboratory analyses will be based on normalised values, i.e., for a given laboratory parameter, values will be transformed to a standard unit and a standard reference range before statistical analysis.

**CTP:** *Laboratory data will be compared to their reference ranges. Values outside the reference range will be flagged. Additionally, differences from baseline will be evaluated.*

Descriptive statistics of laboratory values over time and for the difference from baseline (see [Section 6.7](#)) will be provided. Frequency tables of changes between baseline and last value on treatment with respect to the reference range will be presented.

Possibly clinically significant abnormal laboratory values are only those identified either in the Investigator's comments or at the RPM/DBLM at the latest. It is the Investigator's responsibility to decide whether a lab value is clinically significant abnormal or not. Standard or project-specific rules for flagging clinically significant values in an automated manner will not be applied in this study.

Clinically relevant findings in laboratory data will be reported as baseline conditions (at screening) or as AEs (during the trial) if judged clinically relevant by the investigator, and will be analysed as such.

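### Abstinence from alcohol is not required for the last 2 to 8 days before the final safety laboratory, which the SAP normally treats as the last on-treatment value

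*Protocol*

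**What the plan says.** Protocol Section 4.2.2.2 puts alcohol in one clause with grapefruit, Seville orange and dietary supplements. These "are not permitted starting 7 days before the first administration of trial medication until after the last PK sample is collected". In the flow chart the last row with a PK mark is Day 40 (936:00 h), and that row has no safety laboratory.

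The EOT visit is on Day 42 to 48 and has a safety laboratory but no PK sample. Flow chart footnote 4 confirms the content: "End of trial examination includes physical examination, body weight, vital signs, ECG, safety laboratory, recording of AEs and concomitant therapies". Protocol Section 6.1 gives the same window for the "end-of-trial evaluation (within 14 to 20 days after last drug administration"). The routine panel in Table 5.2.3: 1 includes AST, ALT, GGT, bilirubin and, among the substrates, "Total cholesterol Triglycerides".

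Two other restrictions in Section 4.2.2.2 last longer. For exercise: "Excessive physical activity (such as competitive sport) should be avoided starting 7 days before the first administration of trial medication until the EOT examination". Nicotine is restricted until the study is completed.

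SAP Section 6.7 defines the laboratory baseline as the last available value before first dosing. SAP Table 6.1: 1 runs the on-treatment phase to the end of the trial termination date. SAP Section 7.8.2 then states: "Frequency tables of changes between baseline and last value on treatment with respect to the reference range will be presented".

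**The concern.** The last scheduled safety laboratory, and the only one after Day 30, is taken once the alcohol restriction has lapsed. The pre-dose value it is compared with is taken while the restriction is in force. Men drinking up to 30 g of alcohol per day are eligible (exclusion criterion 16), so some volunteers may resume drinking before EOT.

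Hepatic injury is the trial's only adverse event of special interest (AESI). All adverse events up to trial termination count as on treatment, because the residual effect period is not known (protocol Section 5.2.2.2). A late rise in a liver enzyme or triglycerides would then have a competing explanation that the protocol itself permits. The error could go either way: a shift caused by drinking may be put down to the drug, or a real late change may be put down to drinking.

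**Working it through.** This is calendar arithmetic; no power or sample-size formula applies.

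**Inputs**
- Flow chart: last dose at 648 h, laboratory visit at 696 h, last PK sample at 936 h, EOT on Day 42 to 48.
- Flow chart footnote 7: pre-dose safety laboratory within 3 days before first dose. The flow chart also shows pre-dose visits at -48 h and -2 h.
- Section 4.2.2.2: restriction starts 7 days before first dose.
- Section 6.1: EOT 14 to 20 days after the last dose.

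**Step 1: reproduce the plan's EOT window.** Trial day = hours/24 + 1.
- 648/24 + 1 = Day 28
- 696/24 + 1 = Day 30
- 936/24 + 1 = Day 40
- EOT = 28 + 14 = Day 42 to 28 + 20 = Day 48, which matches the flow chart.

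**Step 2: gap without restriction before the EOT laboratory.**
- Shortest: 42 - 40 = 2 days
- Longest: 48 - 40 = 8 days

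**Step 3: required abstinence at each laboratory.** Days = 7 + (hours from first dose)/24.

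| Sample | Calculation | Required abstinence |
|---|---|---|
| Pre-dose, 3 days before | 7 - 3 | 4 days |
| Pre-dose, -48 h | 7 - 2 | 5 days |
| Pre-dose, -2 h | 7 - 2/24 | 6.9 days |
| Day 30 | 7 + 29 | 36 days |
| EOT | restriction lapsed 2 to 8 days earlier | none required at sampling |

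**Step 4: which value enters the shift table.** The on-treatment phase in SAP Table 6.1: 1 closes at 0:00 on the day after trial termination, and protocol Section 7.3.3 assigns measurements the same way. For a completer the EOT sample falls inside that phase and is later than Day 30. It is therefore normally the last on-treatment value.

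**Step 5: is alcohol checked at EOT?** Breath tests are scheduled at screening and Day -1 only (flow chart footnote 5). Footnote 1 to Table 5.2.3: 2 allows repeats at the investigator's discretion.

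**Step 6: effect of extending the restriction to EOT.** The gap falls from 2-8 days to 0. Required abstinence at EOT becomes 7 + 41 = 48 to 7 + 47 = 54 days.

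**The case against.** Several objections stand and limit the point.

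- **No evidence of drinking.** A reader might infer that the EOT values are taken from men who have resumed alcohol. The documents show only that abstinence is no longer required.
- **Baseline is not long abstinence.** A reader might assume at least 7 alcohol-free days at baseline. The requirement gives about 4 to 6.9.
- **Extending the restriction does not equalise duration.** EOT would follow 48 to 54 days of required abstinence, against 4 to 6.9 at baseline. Day 30 already has a similar mismatch, at 36 days. What the extension does is put every scheduled safety laboratory from baseline onwards under the same rule.
- **The contrast with placebo is not systematically biased.** Placebo subjects follow the same visits and restrictions, so the comparison gains noise only.
- **Reach into the AESI and the primary endpoint is limited.** A reader might conclude that hepatic-injury counts or drug-related adverse events are compromised. The AESI thresholds in Section 5.2.2.1 are multiples of the upper limit of normal and do not use baseline. A laboratory value reaches the primary endpoint only if the blinded investigator judges it clinically relevant and drug-related.
- **Attribution is harder but not impossible.** Breath tests may be repeated, causality assessment weighs confounders and alternative causes, and clinically relevant abnormal values are followed up (Section 6.2.3). Laboratory values are also summarised over time, so the Day 28 and Day 30 results remain visible.

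It can also be argued that the alcohol clause is simply a PK-period restriction. The protocol gives no reason for any of the end dates, so the longer exercise restriction does not prove an intention to standardise EOT. It does show that a restriction running to EOT is already part of this protocol.

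**Conclusion.** The gap is real and minor. For 2 to 8 days before the last safety laboratory, abstinence is not required and no alcohol test is scheduled, yet that value normally closes the shift from a baseline taken under restriction. The consequence is avoidable noise in within-group shift tables and weaker attribution of individual late liver or lipid changes.

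The size of any effect cannot be stated: the number of drinkers and the response of the analytes to 2 to 8 days of drinking are not in the documents. That recent drinking can move some of these values is an assumption. One event is 1/9 = 11.1 percentage points in an active group and 1/12 = 8.3 points in pooled placebo, but this holds for any single event and does not measure an alcohol effect.

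The conclusion assumes a subject who completes the schedule, a non-missing EOT sample, and Day 40 as the last PK sample. Flow chart footnote 9 allows samples to be added, which could shorten the gap, and early discontinuers would differ. It also relies on reading flow-chart columns that are partly removed in the public copy; the Day 40 and EOT rows read consistently.

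**What to change.** Reconcile the end of the alcohol restriction in Section 4.2.2.2 with the EOT safety laboratory. One way is to take alcohol out of the clause tied to PK sampling and end it at the EOT examination, alongside the exercise restriction. The grapefruit, Seville orange and supplement restrictions can stay tied to the last PK sample.

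The cost is one sentence in the protocol and 2 to 8 more days without alcohol for each volunteer, with no extra visit, sample or staff.

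If conduct can no longer change, add to SAP Section 7.8.2 a second shift table that uses the last value taken under the restriction (Day 30) beside the planned one. That costs one additional table.

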5.2.2.2 Adverse event collection and reporting

AE Collection

Upon enrolment into a trial, the subject's baseline condition is assessed (for instance, by documentation of medical history/concomitant diagnoses), and relevant changes from baseline are noted subsequently.

[figure not shown]
Subjects will be required to report spontaneously any AEs as well as the time of onset, end, and intensity of these events. In addition, each subject will be regularly assessed by the medical staff throughout the clinical trial and whenever the investigator deems necessary. As a minimum, subjects will be questioned for AEs (and concomitant therapies) at the time points indicated in the [Flow Chart](#). Assessment will be made using non-specific questions such as 'How do you feel?'. Specific questions will be asked wherever necessary in order to more precisely describe an AE.

A careful written record of all AEs shall be kept by the investigator in charge of the trial. Records of AEs shall include data on the time of onset, end time, and intensity of the event as well as any treatment or action required for the event and its outcome.

The following must be collected and documented on the appropriate eCRF by the investigator:

Proprietary confidential information © 2017 Boehringer Ingelheim International GmbH or one or more of its affiliated companies

- From signing the informed consent onwards through the Residual Effect Period (REP), until individual subject's EOT:
 - all AEs (serious and non-serious) and all AESIs.
 - The only exception to this rule are AEs (serious and non-serious) and AESIs in Phase I trials in healthy volunteers, when subjects discontinue from the trial due to screening failures prior to administration of any trial medication. In these cases, the subjects' data must be collected at trial site but will not be entered in the CRF or trial database and will not be reported in the CTR.
- After the individual subject's EOT:
the investigator does not need to actively monitor the subject for AEs but should only report relevant SAEs and relevant AESIs of which the investigator may become aware of.

The REP for BI 1467335, when measurable drug levels or PD effects are still likely to be present after the last administration, is not known at this early stage of development. Therefore, all AEs reported until the trial termination date (last per protocol contact) will be considered on treatment; please see [Section 7.3.3](#).

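### No AE questioning is scheduled at the attended Day 36 and Day 40 visits, so 10 to 16 days of follow-up pass without a planned enquiry although the residual effect period is unknown

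*Protocol*

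**What the plan says.** **Rule on asking.** Flow Chart footnote 6: "AEs and concomitant therapies will be recorded throughout the trial, but will be specifically asked for at the time points indicated" in the chart. Protocol Section 5.2.2.2 gives the chart the same role: "As a minimum, subjects will be questioned for AEs (and concomitant therapies) at the time points indicated in the" Flow Chart. The chart therefore sets the minimum questioning schedule.

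**Schedule after the last dose.** The three ambulatory visits that follow Day 30 appear as "32+-1 744:00 09:00 Ambulatory visit ¹⁷", "36+-2 840:00 09:00 Ambulatory visit ¹⁷" and "40 936:00 09:00 Ambulatory visit". The AE and concomitant-therapy column is marked on Days 30 and 32 and at EOT, and is empty on Days 36 and 40. Those two visits carry sampling marks only, with no safety laboratory, ECG or vital-signs mark. Footnote 4 confirms that AEs are covered at EOT: "End of trial examination includes physical examination, body weight, vital signs, ECG, safety laboratory, recording of AEs and concomitant therapies". Section 6.1 places EOT "within 14 to 20 days after last drug administration".

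**What is counted.** The primary endpoint is the number and percentage of subjects with drug-related AEs (protocol Section 5.2.1). Section 5.2.2.2 says that the residual effect period is not yet known and that, for this reason, "all AEs reported until the trial termination date (last per protocol contact) will be considered on treatment". SAP Section 6.1 implements this by running the on-treatment phase to the end of the trial termination date.

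**Other routes of collection.** Section 5.2.2.2 also requires subjects to report AEs unprompted, with onset, end and intensity, and says in general terms that medical staff assess them throughout.

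**The concern.** The protocol extends the counting period to trial termination because effects may outlast dosing, but it plans no question for most of that extension. Subjects come to the site twice in the interval and are not due to be asked.

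Day 32 is the natural comparison. In the visible columns its marks match those of Days 36 and 40 except for the AE mark. The visible text gives no reason for treating the three visits differently.

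Three things are at stake:

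- **Ascertainment of the primary endpoint.** Mild or short events after dosing are the ones most easily forgotten if nobody asks until EOT.
- **Onset dating and causality.** The causality guidance in Section 5.2.2.1 uses time to onset and the course of the event after withdrawal. Dates recalled up to about two weeks later are a weaker basis for both.
- **Concomitant therapy.** The same column covers it. Section 4.2.1 in principle allows none, yet it goes unasked while samples are still drawn on Days 36 and 40.

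**Working it through.** **Inputs**

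- Last dose: Day 28, 648:00 h (Flow Chart).
- Days with AE questioning after the day of the last dose: 29, 30, 32 ±1, and EOT on Day 42 to 48 (Flow Chart).
- Attended visits without AE questioning: Day 36 ±2 and Day 40 (Flow Chart).
- EOT window: 14 to 20 days after the last dose (Section 6.1).
- Nine subjects per active group (Section 3.1).

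**1. Check of the plan's own days.** Day = hours/24 + 1.

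- 744/24 + 1 = 32
- 840/24 + 1 = 36
- 936/24 + 1 = 40
- EOT from Section 6.1: 28 + 14 = 42 and 28 + 20 = 48, which agrees with the Flow Chart.

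**2. Are the blanks real?** The Day 30, 32, 36, 40 and EOT rows each have 12 fields as extracted. The last field, the AE column, holds a mark on Days 30 and 32 and at EOT, and is empty on Days 36 and 40.

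**3. Gap without scheduled questioning**

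- Nominal: 42 − 32 = 10 days to 48 − 32 = 16 days.
- With the Day 32 ±1 window: 42 − 33 = 9 days to 48 − 31 = 17 days.

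**4. Share of the follow-up after the last dose (nominal)**

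- EOT on Day 42: 10/(42 − 28) = 10/14 = 71%.
- EOT on Day 48: 16/(48 − 28) = 16/20 = 80%.

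For comparison, the longest interval between AE-questioning days during home dosing is Day 7 to Day 14, which is 7 days.

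**5. Gaps if Days 36 and 40 were marked**

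| Interval | Nominal (days) | With windows (days) |
|---|---|---|
| Day 32 to Day 36 | 4 | 34 − 33 = 1 to 38 − 31 = 7 |
| Day 36 to Day 40 | 4 | 40 − 38 = 2 to 40 − 34 = 6 |
| Day 40 to EOT | 2 to 8 | 2 to 8 |

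The longest possible gap falls from 16 days (17 with the window) to 8.

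**6. Weight of one subject.** 1/9 = 11.1 percentage points on the primary endpoint in an active group. This is the size of one count, not an estimate of how many would be lost.

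**The case against.** **AEs are still collected.** Section 5.2.2.2 requires all AEs to be documented from consent to EOT, asks for spontaneous reports, provides for staff assessment throughout, and calls the chart a minimum. EOT questioning looks back over the whole interval. This stands, and it limits the point. A reader might infer that Days 33 to 41 lie outside AE collection, and the documents do not support that. The mitigations do not remove the point, however. They apply equally on Day 32, where the question is still scheduled, and the general statement on staff assessment is not tied to Day 36 or Day 40.

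**The table is broken in places.** Some treatment-period rows have marks shifted by a column, and some sampling columns are redacted. This is a fair caution. The five post-treatment rows are nevertheless alike in structure and differ in the AE field, so the blanks are very probably real. A look at the original chart would settle it.

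**The endpoint may not move.** For the count to change, a drug-related AE would have to start after Day 32, go unreported at two visits, be forgotten at EOT, and occur in a subject not already counted. The documents give no probability for this. The trial is descriptive (Section 7.2), and placebo subjects follow the same schedule. All of this is correct, so the 11.1 points must not be read as an expected loss.

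**Days 7 and 15.** A reader might see the same omission at the discharge times on these days, which carry no AE mark. The documents do not support treating it as the same problem. Both visits already have AE questioning before dosing, at 144:00 and 336:00. A mark at 145:00 would change the interval to the next question (310:00) from 166 h to 165 h. A mark at 337:00 would change the interval to 480:00 from 144 h to 143 h. Those gaps exist because no visit falls between.

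**Conclusion.** The point holds as a weakness in ascertainment. No AE or concomitant-therapy questioning is scheduled for 10 to 16 days nominally (9 to 17 with the Day 32 window), 71% to 80% of the follow-up after the last dose, although subjects attend twice in that time. It bears on the primary endpoint because the protocol itself treats the residual effect period as unknown and counts AEs to trial termination.

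The consequence is poorer recall, onset dating and timeliness. The documents contain no contradiction here, no break in AE collection, and no basis for estimating how many events would be missed. No sample-size or power figure is affected, since the trial has none.

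The conclusion assumes that the blank cells on Days 36 and 40 reflect the original chart and that subjects attend those visits as planned. It should be changed because the remedy is almost free.

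**What to change.** In the Flow Chart, mark the AE and concomitant-therapy questioning column in the Day 36 ±2 and Day 40 rows, as is already done on Day 32. No change is needed to Section 5.2.2.2, which refers to the chart, or to the SAP, whose on-treatment phase already covers these days. Nothing needs to be added on Days 7 and 15.

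The cost is one brief, non-specific question at each of two existing contacts, at most 2 × 48 = 96 across the planned 48 subjects. It needs no added visit, sample or staff. If the protocol is already approved, the change goes through the amendment route in Section 8.1 and can be combined with any other amendment.
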